6.1.12 Progression-Free Survival

Progression-free survival (PFS) is defined as the duration of time from start of treatment to time of progression.

6.1.13 **Event-Free Survival**

Event-Free Survival (EFS) is defined as the duration of time from start of treatment to: (1) disease progression; (2) second malignant neoplasm; (3) death regardless of cause; or (4) date of last contact, whichever comes first.

6.2 **Safety/tolerability**

Analyses will be performed for all patients having received at least one dose of study drug. The study will use the CTCAE version 4.03 (download: <http://ctep.cancer.gov/reporting/ctc.html>) for adverse event reporting.

7.0 **ADVERSE EVENTS**

7.1 **Experimental Therapy**

7.1.1

7.2 **Adverse Event Monitoring**

Adverse event data collection and reporting, which are required as part of every clinical trial, are done to ensure the safety of subjects enrolled in the studies as well as those who will enroll in future studies using similar agents. Adverse events are reported in a routine manner at scheduled times during a trial. Additionally, certain adverse events must be reported in an expedited manner to allow for optimal monitoring of the subject's safety and care. Adverse events not requiring expedited reporting will be entered into the eCRF on a monthly basis.

All subjects experiencing an adverse event, regardless of its relationship to study drug, will be monitored until:

- the adverse event resolves or the symptoms or signs that constitute the adverse event return to baseline;
- any abnormal laboratory values have returned to baseline;
- there is a satisfactory explanation other than the study drug for the changes observed; or
- death.

7.2.1 **Definitions**

An adverse event is defined as any untoward or unfavorable medical occurrence in a human research study participant, including any abnormal sign (for example, abnormal physical exam or laboratory finding), symptom, clinical event, or disease, temporarily associated with the subject's participation in the research, whether or not it is considered related to the subject's participation in the research.

Adverse events encompass clinical, physical and psychological harms. Adverse events occur most commonly in the context of biomedical research, although on occasion, they can occur in the context of social and behavioral research. Adverse events may be expected or unexpected.

Severity

Adverse events will be graded by a numerical score according to the defined NCI

Adverse events will be graded by a numerical score according to the defined NCI Common Terminology Criteria for Adverse Events (NCI CTCAE) and Version 5.0. Adverse events not specifically defined in the NCI CTCAE will be scored on the Adverse Event log according to the general guidelines provided by the NCI CTCAE and as outlined below.

- Grade 1: Mild
- Grade 2: Moderate
- Grade 3: Severe or medically significant but not immediately life threatening
- Grade 4: Life threatening consequences
- Grade 5: Death related to the adverse event

Serious Adverse Events

ICH Guideline E2A and the UTSW IRB define serious adverse events as those events, occurring at any dose, which meets any of the following criteria:

- Results in death
- Immediately life-threatening
- Results in inpatient hospitalization or prolongation of existing hospitalization
- Results in persistent or significant disability/incapacity
- Results in a congenital anomaly/birth defect
- Based upon appropriate medical judgment, may jeopardize the subject's health and may require medical or surgical intervention to prevent one of the other outcomes listed in this definition.

Note: A "Serious Adverse Event" is by definition an event that meets **any** of the above criteria. Serious adverse events may or may not be related to the research project. A serious adverse event determination does not require the event to be related to the research. That is, both events completely unrelated to the condition under study and events that are expected in the context of the condition under study may be serious adverse events, independent of relatedness to the study itself. As examples, a car accident requiring overnight hospitalization would be a serious adverse event for any research participant; likewise, in a study investigating end-stage cancer care, any hospitalization or death which occurs during the protocol-specified period of monitoring for adverse and serious adverse events would be a serious adverse event, even if the event observed is a primary clinical endpoint of the study.

*Pre-planned hospitalizations or elective surgeries are not considered SAEs. Note: If events occur during a pre-planned hospitalization or surgery that prolongs the existing hospitalization, those events should be evaluated and/or reported as SAEs.

Information about all adverse events, whether volunteered by the subject, discovered by investigator questioning, or detected through physical examination, laboratory test or other means, will be collected, recorded, and followed as appropriate.

Adverse events that begin or worsen after informed consent should be recorded in the Adverse Events CRF. Conditions that were already present at the time of informed consent should be recorded in the patient's eCRF. Adverse event monitoring should be continued for at least 30 days (or 5 half-lives, whichever is longer) following the last dose of study treatment. Adverse events (including lab abnormalities that constitute AEs) should be described using a diagnosis whenever possible, rather than individual underlying signs and

symptoms. When a clear diagnosis cannot be identified, each sign or symptom should be reported as a separate Adverse Event.

The occurrence of adverse events should be sought by non-directive questioning of the patient at each visit during the study. Adverse events also may be detected when they are volunteered by the patient during or between visits or through physical examination, laboratory test, or other assessments. As far as possible, each adverse event should be evaluated to determine:

1. The severity grade (CTCAE Grade 1-4)
2. Its duration (Start and end dates or if continuing at the Safety Follow-up Visit)
3. Its relationship to the study treatment (Reasonable possibility that AE is related: No, Yes)
4. Action taken with respect to study or investigational treatment (none, dose adjusted, temporarily interrupted, permanently discontinued, hospitalized, unknown, not applicable)
5. Whether medication or therapy was given (no concomitant medication/non-drug therapy, concomitant medication/non-drug therapy)
6. Outcome (not recovered/not resolved, recovered/resolved, recovering/resolving, recovered/resolved with sequelae, fatal, unknown)
7. Whether it is serious, where a serious adverse event (SAE) is defined as in Sections 7.2.1 and 7.4.1.

All adverse events should be treated appropriately. Such treatment may include changes in study drug treatment including possible interruption or discontinuation, starting or stopping concomitant treatments, changes in the frequency or nature of assessments, hospitalization, or any other medically required intervention. Once an adverse event is detected, it should be followed until its resolution, and assessment should be made at each visit (or more frequently, if necessary) of any changes in severity, the suspected relationship to the study drug, the interventions required to treat it, and the outcome.

Information about common side effects already known about the investigational drug can be found in the Investigators' Brochure. This information should be included in the patient informed consent and should be discussed with the patient during the study as needed.

Adverse event monitoring should be continued for at least 30 days following the last dose of study treatment

Laboratory Test Abnormalities

Laboratory abnormalities that constitute an Adverse event in their own right (are considered clinically significant, induce clinical signs or symptoms, require concomitant therapy or require changes in study treatment), should be recorded on the Adverse Events CRF. Whenever possible, a diagnosis, rather than a symptom should be provided (e.g. anemia instead of low hemoglobin). Laboratory abnormalities that meet the criteria for Adverse Events should be followed until they have returned to normal or an adequate explanation of the abnormality is found. When an abnormal laboratory or test result corresponds to a sign/symptom of an already reported adverse event, it is not necessary to separately record the lab/test result as an additional event.

Laboratory abnormalities, that do not meet the definition of an adverse event, should not be reported as adverse events. A Grade 3 or 4 event (severe) as per CTCAE does not automatically indicate a SAE unless it meets the definition of serious as defined below and/or as per investigator's discretion. A dose hold or medication for the lab abnormality may be required by the protocol and is still, by definition, an adverse event.

7.2.2 Unanticipated Problems Involving Risks to Subjects or Others (UPIRSOs):

The phrase “unanticipated problems involving risks to subjects or others” is found, but not defined in the regulations for the HHS regulations at 45 CFR 46, and the FDA regulations at 21 CFR 56.108(b)(1) and 21 CFR 312.66. For device studies, part 812 uses the term unanticipated adverse device effect, which is defined in 21 CFR 812.3(s). Guidance from the regulatory agencies considers unanticipated problems to include any incident, experience, or outcome that meets ALL three (3) of the following criteria:

- Unexpected in terms of nature, severity or frequency given (a) the research procedures that are described in the protocol-related documents, such as the IRB-approved research protocol and informed consent document; and (b) the characteristics of the subject population being studied; **AND**
- Related or possibly related to participation in the research (possibly related means there is a reasonable possibility that the incident, experience, or outcome may have been caused by the procedures involved in the research; **AND**
- Suggests that the research places subjects or others at a greater risk of harm (including physical, psychological, economic, or social harm) than was previously known or recognized. Note: According to OHRP, if the adverse event is serious would always suggest a greater risk of harm.

Follow-up

All adverse events will be followed up according to good medical practices.

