5.2 Procedures During Treatment

- 5.2.1 **Monthly (+/- 7 days):**
 - Physical exam (including neurologic exam), vital signs, performance status
 - Pulse Oximetry
 - CBC with differential
 - Serum Chemistries to include: alkaline phosphatase, ALT, AST, total bilirubin, calcium, phosphorus, BUN, creatinine, total protein, albumin, fasting glucose, potassium, sodium, chloride, bicarbonate, uric acid, LDH, fasting lipid panel (LDL, total cholesterol, triglycerides)
 - PT/PTT/INR
 - Urine pregnancy test for females of childbearing potential (Section 3.2.12)
 - AE Assessment
 - Review of Concomitant Medications
 - Drug Accountability Review
 - Everolimus trough levels will be tested 2 weeks after starting protocol therapy. Repeat testing may be required if there are dose adjustments or other parameters met as defined in Section 5.2.4.
- 5.2.2 **Assessment of Tumor Response:**
 - MRI of the brain and spine: MRI of the brain and spine should be performed every other month for the first year, every third month for the second year, and whenever clinically indicated. Specifically, prior to courses 3, 5, 7, 9, 11, 13, 16, 19, 22, and then at the end of treatment (after course 24). Note: MRI should be completed within 7 days *before* the start of the indicated cycles.
 - Lumbar puncture for cytology: Not required, but to be performed as clinically indicated
- 5.2.3 **Within 30 days after treatment termination:**
 - Physical exam (including neurologic exam), vital signs, performance status
 - CBC with differential
 - Serum Chemistries to include: alkaline phosphatase, ALT, AST, total bilirubin, calcium, phosphorus, BUN, creatinine, total protein, albumin, fasting glucose,

potassium, sodium, chloride, bicarbonate, uric acid, LDH, fasting lipid panel (LDL, total cholesterol, triglycerides).

- PT/PTT/INR
- Urine pregnancy test for females of childbearing potential (Section 3.2.12)
- Hepatitis serology, including HBsAg, HBsAb, HBcAb, Hep C RNA for patients at risk of hepatitis as defined in Section 3.2.14.
- AE Assessment
- Review of Concomitant Medications
- Drug Accountability Review

5.2.4 Pharmacokinetic Drug Monitoring and Adjustments:

The target drug trough level of Everolimus is 5 – 15 ng/ml.

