Neurologic examination is at least stable and maintenance corticosteroid dose is not increased, and MRI meets neither the criteria for MR nor the criteria for progressive disease and must be sustained for at least 8 weeks.

6.1.6.1 Prolonged Stable Disease is defined as stable disease for at least 6 months duration.**6.1.7 Progressive Disease (PD):**

Progressive neurologic abnormalities or worsening neurologic status not explained by causes unrelated to tumor progression (eg, anticonvulsant or corticosteroid toxicity, electrolyte disturbances, sepsis, hyperglycemia, etc), OR a greater than 25% increase in the bi-dimensional measurement on MRI, OR the appearance of a new lesion or new CSF positivity, OR increasing doses of corticosteroids required to maintain stable neurologic status or imaging.

All patients who have measurable disease according to the above response criteria, who received at least 1 cycle of therapy and who have their disease re-evaluated will be evaluable for response. All sites of disease should be followed as either target or nontarget lesions, as categorized at baseline. All measurable lesions up to a maximum of 5 lesions should be identified as target lesions, while all other lesions (either additional measurable lesions or nonmeasurable lesions) should be classified as nontarget lesions. If possible, the same method, radiological or physical, should be employed and assessed by the same individual on each occasion. If possible, the same method should be employed and assessed by the same institution on each occasion. Ideally, any response should be confirmed by repeated evaluation at least 28 days after the first assessment where the response criteria were met.

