9.0 STATISTICAL CONSIDERATIONS

9.1 Study Design/Study Endpoints

The study is a prospective single-arm multi-center phase II study that determines the objective response rate following treatment with everolimus for children with recurrent or progressive ependymomas. Given the relatively small study sample size, descriptive statistics will be used to report the results of the study.

Study endpoints include the following:

- Objective Response Rate = Complete Response Rate + Partial Response Rate + Prolonged Stable Disease Rate.
- Duration of Response
- Progression Free Survival
- Overall Survival
- Dose-limiting toxicities
- Biological markers of mTOR pathway activation, including phosphorylated S6^{235/236}, phosphorylated S6^{240/244}, phosphorylated PRAS40 (pT246), phosphorylated 4EBP1, phosphorylated P70^{S6K}, and PTEN expression.

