9.3 Data Analyses Plans

Objective response rate and the corresponding 95% confidence interval will be estimated using the exact binomial method. Kaplan-Meier method will be used to estimate the duration of response, progression free survival (PFS) and event free survival (EFS) following treatment with everolimus for children with recurrent or progressive ependymomas. The corresponding 95% confidence interval will be computed using Greenwood's formula. Safety and tolerability of everolimus will be estimated using exact binomial method. Exploratory analysis will be conducted to investigate the correlation between response rate and biological markers of mTOR pathway activation, including phosphorylated S6^{235/236}, phosphorylated S6^{240/244}, phosphorylated PRAS40 (pT246), phosphorylated 4EBP1, phosphorylated P70^{S6K}, and PTEN expression.

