APPENDIX II: Time and Events Table

Period/Procedure	Screening	Course 1	Courses 2-24 ¹⁰	End of Treatment Visit ¹³	Long Term Follow Up
Study Day/Visit Day	-14 to 1	Day 14 (+/- 4 days)	Day 1 (+/- 7 days)	Within 30 Days	
Informed Consent	X				
Central Review of Pathology and MRI¹	X				
AE Assessment	X		X	X¹⁴	
Concomitant Medications	X		X	X¹⁴	
Drug Accountability			X	X	
Clinical procedures					
Physical Exam	X		X	X	
Vital Signs	X		X	X	
Medical History	X				
Performance Status	X		X	X	
Neurologic Exam	X		X	X	
Pulse Oximetry²	X		X		
Laboratory procedures					
CBC w/ Diff³	X		X	X	
Blood Chemistry⁴	X		X	X	
Coagulation⁵	X		X	X	
Pregnancy Test (HCG)⁶	X		X	X	
Hepatitis (If Required)^{7,8}	X			X	
Everolimus PK Test⁹		X			
Disease Assessment & Outcomes					
Imaging (MRI)¹¹	X		X*¹¹	X	
Lumbar Puncture (optional)¹²	X		X	X	
Survival Follow Up & Other Treatment					X¹⁵

- 1 Central review of pathology/MRI should be completed concurrently with registration, but is not required before starting therapy.
- 2 If pulse oximetry is less than 93% on room air patient should get a CXR monthly until pulse oximetry is >93%.
- 3 Including CBC with differential
- 4 Including alkaline phosphatase, ALT, AST, total bilirubin, calcium, phosphorus, BUN, creatinine, total protein, albumin, glucose, potassium, sodium, chloride, bicarbonate, uric acid, LDH, and lipid panel (LDL, total cholesterol, triglycerides)
- 5 Including PT/PTT/INR
- 6 For females of child bearing potential, urine or serum pregnancy test as per your institutional guidelines. See Section 3.1.12 for further details.
- 7 Including HBsAg, HBsAb, HBcAb, Hep C RNA. See Protocol Section 3.2.14 for details.
- 8 Patients who test positive for hepatitis B antibodies without receiving prior vaccination will be monitored for HBsAg every 4 weeks.
- 9 PK testing should also be performed 2 weeks post any Everolimus dose adjustment or any CYP3A4 concomitant medication administration/dose adjustment. See Protocol Section 5.2.4 for details.
- 10 Courses are 28 days in length. Each subsequent course following course 1 should begin within 7 days of the end of the prior course.
- 11 MRI of the brain and spine will be performed at the beginning of courses 3, 5, 7, 9, 11, 13, 16, 19, 22, and at the end of treatment visit (after course 24). This assessment should be performed on day 1 of these courses as possible, but may be performed up to 7 days prior to starting these courses if necessary.

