- 12 Lumbar puncture for cytology is optional but may be performed if clinically indicated.
- 13 The End of Treatment Visit should be completed within 30 days of treatment termination.
- 14 Adverse event and concomitant medication monitoring should be continued for at least 30 days following the last dose of study treatment
- 15 Survival follow up will be completed by phone or medical record review.

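### PFS is defined to end at progression only, so a death without documented progression is censored and the Kaplan-Meier estimate is time to progression under the name PFS

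*Combined protocol and SAP*

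**What the plan says.** Section 6.1.12 gives the whole PFS definition in one sentence: "Progression-free survival (PFS) is defined as the duration of time from start of treatment to time of progression". It names no other event and no censoring rule.

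Section 6.1.13, directly below, defines EFS from the same starting point. Its list opens with progression and second malignancy and ends "3) death regardless of cause; or (4) date of last contact, whichever comes first". Death is therefore written into EFS and not into PFS.

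Section 9.3 sets the analysis: "Kaplan-Meier method will be used to estimate the duration of response, progression free survival (PFS) and event free survival (EFS"), with 95% intervals from Greenwood's formula. It does not say what counts as an event or when a patient is censored. The study summary's statistical entry adds nothing on this.

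Elsewhere PFS is only named. Section 2.2.1 lists it as a secondary objective together with duration of response and EFS. The endpoint lists in 2.3 and 9.1 ("Study endpoints include the following") contain PFS and overall survival but not EFS.

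**The concern.** PFS is ordinarily read as time alive without progression. Under 6.1.12 only progression ends it. In a Kaplan-Meier analysis with progression as the sole event, a patient who dies first leaves the risk set as a censored observation. The curve then treats that child as if progression could still be observed later, with the same prospects as the children still at risk. A reader of the report would take the figure for progression-free survival when it is time to progression.

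Such deaths are possible in this trial. Sections 4.5.3 and 4.5.8 describe fatal infections and fatal pneumonitis with this drug. Section 6.1.10 provides for patients who stop treatment for general deterioration without objective progression and reports them in a separate category. The documents do not say how often either would happen.

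At stake is one secondary estimate, its interval, and any comparison of it with PFS figures from other studies. The error can only flatter the result.

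**Working it through.** **The plan's own figures.** No rate, median or precision target is given for PFS. The only design calculation is the Simon two-stage design for ORR in 9.2: stop if 0 of 7 respond, otherwise reject the 10% null with 4 or more responses in 18. Exact binomial summation over stage 1 counts of 1 or more gives type I error 0.0893 and power 0.8000 at 30%, consistent with the stated 10% and 80%. None of this uses PFS.

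**Inputs for PFS.** N = 18 comes from 9.2. The number M of patients with a first event (progression or death) by month 6, and how many of those events are deaths without documented progression, are assumptions. No ties and no other censoring before month 6 are assumed.

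**Formula.** Counting every first event, the product of (1 − 1/n) over the M events reduces to S = (18 − M)/18. If the i-th first event is a death that is censored, its factor drops out. The number at risk there is 19 − i, so

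S* = (18 − M)/18 × (19 − i)/(18 − i).

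The multiplier always exceeds 1, so the curve cannot fall. It is smallest when the death comes first (18/17) and largest when it comes last, where S* = (19 − M)/18, a gain of 1/18 = 5.6 points.

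**One such death, M = 12.** S = 6/18 = 33.3%.
- Death first: 33.3% × 18/17 = 35.3%.
- Death last: 33.3% × 7/6 = 38.9%.
- Mean over the 12 positions: 33.3% × [1 + (1/6 + … + 1/17)/12] = 33.3% × (1 + 1.1562/12) = 36.5%.

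**Two such deaths, M = 12.**
- First two events: 33.3% × 18/17 × 17/16 = 37.5%.
- Last two events: 33.3% × 8/7 × 7/6 = 44.4%.
- Mean over all 66 pairs: 40.1%.

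**Other event counts, same formula.**

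| First events by month 6 | All deaths counted | One death censored: range (mean) | Shift in points (mean) | Two deaths censored: mean |
|---|---|---|---|---|
| 9 | 50.0% | 52.9–55.6% (54.0%) | +2.9 to +5.6 (+4.0) | 58.3% |
| 12 | 33.3% | 35.3–38.9% (36.5%) | +2.0 to +5.6 (+3.2) | 40.1% |
| 15 | 16.7% | 17.6–22.2% (18.8%) | +1.0 to +5.6 (+2.2) | 21.2% |

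A death after month 6 does not move the 6-month figure, although it does affect the later curve.

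**Cross-check with constant hazards.** If a share s of first events are such deaths, the estimated curve is S raised to the power (1 − s), and the median is multiplied by 1/(1 − s). With a true median of 6 months (assumed), s = 5%, 10%, 20% and 30% give medians of 6.3, 6.7, 7.5 and 8.6 months. The 6-month estimates are 51.8%, 53.6%, 57.4% and 61.6%, against a true 50%.

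**The case against.** The best reply is that the plan largely covers itself. EFS counts death, belongs to the same secondary objective and gets the same Kaplan-Meier analysis. Overall survival is a listed endpoint. Adding death to PFS would make it almost identical to EFS, differing only by second malignancy. This stands as a limit on severity, and it is why renaming the endpoint is a legitimate alternative. It does not make the label in 6.1.12 correct, and the lists in 2.3 and 9.1 carry PFS without EFS.

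Second, qualifying deaths may be few. Under 6.1.7 progression includes "Progressive neurologic abnormalities or worsening neurologic status not explained by causes unrelated to tumor progression", and also a rising steroid requirement. Neurologic examination is monthly, and MRI is every other month in the first year (5.2). This stands: the shift may be zero.

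Third, the shift is small beside sampling error. At 33.3% with 18 patients and no earlier censoring, the standard error is √(0.333 × 0.667/18) = 0.111, so the interval is about 12% to 55%. That is also true, but the shift has a known direction and costs one sentence to remove.

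A reader might go further and infer that EFS is overstated too, because follow-up after treatment is described mainly for survival. The documents do not support a figure for that. Appendix II collects other treatment and allows record review, so later progression may well be found. The 8.7 to 24 months in 1.1 is not stated to be a median or to run from start of treatment, so it cannot anchor a calculation. Appendix II places an MRI "at the end of treatment visit (after course 24"), and 5.2.3 does not list one. Whether early discontinuers have that scan is a separate scheduling question that does not bear on the PFS definition.

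**Conclusion.** The point holds. Section 6.1.12 states a rule, no other section adds death to it, and Kaplan-Meier under that rule estimates time to progression. The censoring of deaths is not written out; it follows from having progression as the only event.

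On the assumed event counts (9 to 15 first events among 18 patients by month 6), one death without documented progression in that period adds 1.0 to 5.6 points to the 6-month figure. The mean over orderings is about 2 to 4 points. With no such death there is no change. The direction is certain and the frequency is unknown.

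It would be wrong to infer that the trial's conclusion is at risk. PFS is secondary and, under 9.1, reported descriptively. The ORR hypothesis test, both stage rules and the sample size do not depend on it. Nor should one infer that last contact is meant as an EFS failure: in a Kaplan-Meier analysis it reads most naturally as the censoring date, and only the wording needs tidying.

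**What to change.** Amend 6.1.12 in one of two ways before the analysis.

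1. Define PFS as time from start of treatment to progression or death from any cause, whichever is first. Censor patients with neither at the last disease assessment that showed no progression.
2. Keep the present endpoint but call it time to progression wherever PFS is named (study summary, 2.2.1, 2.3, 6.1.12, 9.1, 9.3), and state that deaths without progression are censored. Rely on EFS for the death-inclusive estimate, and add EFS to the lists in 2.3 and 9.1.

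As an editorial clarification, take the last-contact date out of the numbered EFS list in 6.1.13 and label it as censoring.

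The cost is a wording amendment with IRB approval under 10.7. It needs no extra patients and no change to treatment or to the ORR design. The downside of the first option is a possibly less favourable PFS figure. Making the choice before the data are analysed keeps it from depending on the result.
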